8.3.3 Subject Withdrawal Criteria

A subject may withdraw from the study at any time for any reason.

A subject will be withdrawn from the study if his/her safety or well-being is determined to be at risk. Withdrawal will be made at the discretion of the investigator or at the subject's request.

A subject must withdraw from the study for any of the [following](#) reasons:

- The subject or legal representative withdraws consent
- The subject's product code is unblinded
- There is a significant protocol violation

A subject may be withdrawn from the study for any of the following reasons:

- Lost to follow-up
- Investigator discretion

Withdrawal is permanent; after a subject has been withdrawn, he/she will not be allowed to enroll again.

If a subject is withdrawn from the study for any reason, the End of Study or Early Termination procedures (Visit 5/Week 24) should be completed and any outstanding data and study product should be collected. Data, including the date and primary reason for withdrawal, must be documented on the End of Study case report form (CRF) and source document.

If a subject withdraws from the study at any time due to an AE, the reason for withdrawal, the nature of the AE, and its clinical course must be fully documented. The investigator must strive to follow the subject until the AE has resolved, become clinically insignificant, is stabilized, or the subject is lost to follow-up. For any SAE, follow procedures provided in [Section 8.9.5](#)

8.3.4 Replacement of Subjects

A subject who withdraws from the study will not be replaced.

8.4 Treatments

The investigator will take responsibility for and will take all steps to maintain appropriate records and ensure appropriate supply, handling, storage, distribution, and use of study materials in accordance with the protocol and any applicable laws and regulations.

8.4.1 Dosage and Formulations

The test and comparator products will be provided by the sponsor as follows.

Test product: Revanesse Ultra +: a clear, colorless gel in 1.0 mL pre-filled syringes with 25 mg/mL of stabilized hyaluronic acid and lidocaine 0.3% w/w.

Comparator product: Revanesse Ultra: a clear, colorless gel in 1.0 mL pre-filled syringes with 25 mg/mL of stabilized hyaluronic acid.

8.4.2 Method of Treatment Assignment, Randomization, and/or Stratification

Every subject will receive Revanesse Ultra + on one side of the face and Revanesse Ultra on the other side of the face. The side of the face treated with either product will vary from subject to subject based on the randomization assignment made at Visit 1/Day 1.

Subjects who satisfy all of the inclusion and none of the exclusion criteria will be randomized with respect to which side of the face receives which treatment. Randomization will be performed according to a computer-generated randomization scheme. The randomization scheme will be generated and maintained by an independent third party. A sealed copy of the

randomization scheme should be retained at each site and should be available to regulatory authorities at the time of site inspection to allow for verification of the treatment identity for each subject.

A unique subject number will be assigned to each subject. Each site will receive a list of randomization code numbers and corresponding study product boxes. Each eligible subject will be assigned a unique randomization code number in ascending order.

No stratification based on age, sex, or other characteristics will be performed.

8.4.3 Administration of Dose for Each Subject

Subjects are physically masked (blindfolded) just prior to and during all injection procedures to prevent observation of the syringes containing study product.

Injections of the study product are performed by the unblinded injecting investigator. The blinded evaluator is not allowed to retrieve study supplies or to be present during opening of the study supplies or during the injections. The injecting investigator is not to have any discussion with the blinded evaluator or subjects regarding the treatments.

Up to a maximum of 2.0 mL (2 pre-filled syringes) will be used per treatment on each nasolabial fold similar to the comparator agent based on previous studies and common clinical practice.

The injection will be given intradermally and for best results should be injected in the mid-dermis. The treatment technique and the volume per treatment should be as similar as possible on both sides of the face.

For many subjects with moderate NLFs, one syringe will be adequate per NLF. Based on the iGAI score at that time, a touch-up treatment may be administered at Visit 2/Week 2.

For this study, topical anesthetic will not be used. Ice may be applied before the treatment if the injecting investigator deems it necessary. The same technique should be used on both sides of the face. Using the nondominant hand to apply gentle downward traction to the inferiormost aspect of the fold to immobilize it, the dominant hand is used to inject filler. Steadying the injecting hand on the mandible or the other hand, the linear threading technique is most easily used to deposit the filler beneath the fold and efface it.

The peri-alar sulcus, a triangular shaped concavity at the upper end of the fold, may be more effectively filled with the fanning technique of implantation, where two or three threads are deposited in a fan-like array. Wide portions of the fold may require several threads placed side by side, with gentle massage after each thread is placed.

Treatment of this area is generally easy and straightforward. Notice that the fold is partially formed by prominent cheek tissue that is lateral to it, with the fold becoming more prominent as the cheek becomes more protuberant. Therefore, injections should stay medial to the fold to fill it. Injecting lateral to the fold, in the excessive cheek tissue, can actually tend to accentuate the fold.

Bruising is the most common side effect in this area and usually resolves in 5 to 7 days. The facial artery runs below the fold and necrosis is possible, although rare.

Implantation Technique

After removing any make-up, the area to be treated should be cleansed with an alcohol prep pad or some other antiseptic. It is useful to avoid having the subject completely recline as the contours of some facial folds change in the supine position.

The viscosity of stabilized HA gel fillers decreases with increasing temperature. The syringe should be warmed in the hand for a few minutes prior to injection. Use the syringes labeled LEFT to treat the left NLF and the syringe labeled RIGHT to treat the right NLF.

Before injecting the subject, push the plunger forward to feel the intrinsic resistance of the filler moving through the needle, until a small droplet appears at the needle tip. Wipe off the droplet with a sterile pad and begin injection.

The linear threading technique is probably the most commonly used. Holding the syringe parallel to the length of the NLF to be treated, pierce the skin and advance the needle to its fullest extent. Then, while slowly withdrawing the needle, apply even pressure on the plunger to dispense material into dermis. Relieve pressure just before withdrawing the needle from the skin to avoid leakage. Several successive “threads” below, above, or beside previous injections may be required to fill larger folds.

Enter the skin with a needle angle of 30°, 45°, or parallel to the skin. It is recommended to keep the needle bevel up so the tip of the needle is seen and more precisely controlled where the skin is pierced. Keep the tip of the needle at constant depth during implantation, depositing all filler material within the same plane to get even results. The depth of needle placement (and thus filler implantation) should be mid-dermis for NLFs, where the needle’s contour should be visible through the subject’s skin, but the needle’s color is not visible.

After injection, manually massage the area gently to smooth out any nodular or uneven areas, and ensure the implanted material conforms to the contour of surrounding tissues. Using an ice pack or other cold compress can help to minimize swelling and alleviate post injection discomfort.

The subject should be injected so that an optimal correction is achieved. If overcorrected, massage firmly between fingers or against underlying bone to obtain optimal results. Approximately 20% overcorrection can be massaged out; more will lead to a persistent unwanted cosmetic result.

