8.4.7 Prior and Concomitant Medications/Treatments

All medications and other treatments taken by the subject within 6 months before Visit 1/Day 1 and during the study are to be recorded on the CRF using their generic name, if known, with the corresponding indication. The medications to be recorded include prescription and OTC medications and dietary supplements. All medications taken on a regular basis, including vitamins, aspirin, and acetaminophen, should be recorded prior to first use of the study medication.

The use of any concomitant medication must relate to the subject's documented medical history, prophylaxis, or an AE.

8.4.7.1 Medications, Supplements, and Other Substances Prohibited Before Study Entry and During the Study

The medications prohibited prior to Visit 1/Day 1 are listed in the exclusion criteria ([Section 8.3.2](#)).

Subjects will be advised to avoid the following for the duration of the study:

- Botox® in the study treatment areas
- Any chemical peel (light, medium or deep) in the study treatment areas
- Soft tissue augmentation anywhere on the face
- Dermabrasion or laser abrasion anywhere on the face
- Silicone injections or implants anywhere on the face
- Facial wrinkle therapies, including Accutane® and Renova®
- Aesthetic facial surgery (i.e., facelift)
- Oral corticosteroids or immunosuppressive medications
- Topical corticosteroids on the face
- Treatment with intense pulsed light

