8.4.7.2 Concomitant Medications, Supplements, and Other Substances Allowed During the Study

Permitted medications/treatments include any concomitant medication/treatment not listed in the exclusion criteria ([Section 8.3.2](#)).

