8.6.7 Visual Analog Scale for Pain (VAS)

Pain from the injection will be assessed at each NLF by the subject using a 100-mm VAS scale from 0 = no pain to 100 = worst possible pain (Figure 1) at Visit 1/Day 1 immediately after the injection and 15, 30, 45, and 60 minutes post injection. At Visit 2/Day 14, this assessment will be performed for subjects who do not have a touch-up treatment and prior to touch-up, immediately after the injection and 15, 30, 45, and 60 minutes post injection for subjects who do have a touch-up treatment. Subjects will be asked the question “How would you rate your pain from the injection of study material?” and will respond by placing a mark on the VAS.

Figure 1 Visual Analog Scale for Subject Assessment of Pain Following Injection

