8.8 Efficacy Assessments

8.8.1 Primary Efficacy Endpoint

The primary efficacy endpoint is the proportion of responders immediately after injection, where a responder is defined as a subject who had a within-subject difference (Revanesse Ultra – Revanesse Ultra +) in VAS pain score of at least 10 mm.

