8.8.2 Secondary Efficacy Endpoints

Secondary efficacy endpoints are the proportion of responders at 15, 30, 45, and 60 minutes post injection and at 2 weeks post injection (prior to touch-up).

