## 6 Tables and Listings

The following is an example of tables and listings that will be included in the clinical study report. Tables and listings may be modified as needed during the data analyses.

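### Protocol 8.4.3 suggests cold after injection to ease discomfort but does not place it after the Day 1 pain scores, so the 15–60 minute estimates are open to it

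*Protocol*

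**What the plan says.** Under Implantation Technique, directly after the instruction to massage the treated area, Protocol 8.4.3 adds: "Using an ice pack or other cold compress can help to minimize swelling and alleviate post injection discomfort". It gives no time, no side and no decision-maker.

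Pain is scored by the subject for each fold on Day 1 "immediately after the injection and 15, 30, 45, and 60 minutes post injection" (Protocol 8.6.7). The primary endpoint is the immediate one: "The primary efficacy endpoint is the proportion of responders immediately after injection" (8.8.1). The same-day secondaries follow: "Secondary efficacy endpoints are the proportion of responders at 15, 30, 45, and 60 minutes post injection" (8.8.2). A responder has a comparator-minus-test difference of at least 10 mm.

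These texts bear on how cold is used:

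- **Technique.** Protocol 8.4.3 bars topical anesthetic and lets the injecting investigator, who is unblinded, use ice before treatment. The next sentence asks for one technique on both sides. An earlier sentence in the section says: "The treatment technique and the volume per treatment should be as similar as possible on both sides of the face".
- **Permission.** Protocol 8.4.7.2: "Permitted medications/treatments include any concomitant medication/treatment not listed in the exclusion criteria". Ice is not listed there.
- **Recording.** Protocol 8.4.7: "All medications and other treatments taken by the subject within 6 months before Visit 1/Day 1 and during the study are to be recorded". SAP Listing 16.2.9.2 has columns for face side and for start and stop date.

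The flow-chart footnotes, the VAS section, the Visit 1 steps and the prohibited list do not mention cold after injection.

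**The concern.** The trial measures pain after injection, and the plan suggests a second pain-relieving measure inside the hour in which that pain is scored. The effect depends on where the cold goes:

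- On the comparator fold only, it lowers the difference and the responder rate.
- On the test fold only, it raises both.
- On both folds equally, it leaves the difference alone if it removes the same number of millimetres from each score. It shrinks the difference if it cuts each score in proportion, and fewer subjects then reach 10 mm.

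At stake is whether the 15–60 minute responder rates describe lidocaine alone or lidocaine plus variable aftercare. The 2-week score is not affected by Day 1 icing in any evident way.

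**Working it through.** **1. The plan's own figures.** The rule is that the exact 95% lower limit must exceed 50%. With 80 subjects the limit is 0.497 at 49 responders and 0.510 at 50, so success needs 50 of 80. P(X ≥ 50) is 94.1% at a true rate of 70% (stated 94.1%) and 87.9% at 68% (stated 87.8%). The plan's power reproduces to within 0.1 point.

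**2. Inputs.** From the comparator-filler study in Protocol 9.6, Table 2: 28/60 = 46.7% at 15 minutes and 17/60 = 28.3% at 30 minutes. The primary planning rate is 70%. Everything about ice is assumed, because the documents give no figure: a normal within-subject difference D with SD 20–30 mm; for one-sided icing, a 10 mm fall on one fold in a fraction f = 10–25% of subjects; for equal icing, every subject iced and both scores cut by 10% or 20%.

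**3. Formulas.** Set the mean so that P(D ≥ 10) = p0, giving mean = 10 + z(p0) × SD.

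- Comparator fold iced: p = (1 − f) × p0 + f × P(D ≥ 20).
- Test fold iced: p = (1 − f) × p0 + f × P(D ≥ 0).
- Both folds, fraction c of each score kept: p = P(D ≥ 10/c).

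Example at 15 minutes, SD 20, f = 0.25: the mean is 10 − 0.0837 × 20 = 8.33 and P(D ≥ 20) = 0.280, so p = 0.75 × 0.467 + 0.25 × 0.280 = 0.420. With the test fold iced, P(D ≥ 0) = 0.661 and p = 0.515. Equal icing with c = 0.9 gives P(D ≥ 11.11) = 0.445.

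**4. Secondary estimates** (ranges over SD, and over f for one-sided icing).

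| | 15 min | 30 min |
|---|---|---|
| No cold before the score | 46.7% | 28.3% |
| Comparator fold only | 42.0–45.4% | 24.8–27.3% |
| Test fold only | 48.0–51.5% | 29.6–33.0% |
| Both folds, 10% cut | 44.5–45.2% | 26.5–27.1% |
| Both folds, 20% cut | 41.7–43.4% | 24.3–25.6% |

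**5. Secondary decisions.** At 15 minutes P(X ≥ 50) is 0.3% with no cold, 0.02–0.15% with the comparator fold iced and 0.6–3.2% with the test fold iced. Equal icing lowers it. At 30 minutes it is below 1 in 10 million in every row. Testing stops at the first failure (Protocol 9.4, SAP 5.1), so on these rates the later tests would hardly ever be reached.

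**6. Primary, only if cold comes before the immediate score.** From 70%, the same one-sided model on the comparator fold gives 65.2–68.8% and power of 73.9–90.6%. Equal icing with a 10% cut gives 68.0–68.7% and 88.1–90.4%. These figures are conditional on a sequence that the plan neither requires nor describes.

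**The case against.** The best counter-text is the sentence in 8.4.3 asking for one technique on both sides. It directly follows the sentence on pre-treatment ice, so a site would naturally handle cold equally on both folds. That stands, and it takes most of the force from the one-sided scenarios. It does not cover timing, and equal cold can still shrink the difference.

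The primary score is meant to be immediate, and icing first would delay it. That also stands: the text leaves this open, but the schedule works against it. The suggestion itself is permissive technique advice, and nothing shows that any site iced within the hour.

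A reader might infer that an unblinded injector could use ice to favour the test product. The documents do not support this. They do not say who decides on cold after injection, and icing in response to pain would more plausibly reach the fold without lidocaine, which works against the superiority claim.

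A reader might also infer that ice would go unrecorded, or that its order against the scores could not be recovered. Recording as another treatment is already required. The injection and VAS listing shells carry clock times while the intervention shell shows dates only, but SAP Section 6 says "Tables and listings may be modified as needed during the data analyses", and the CRF is not among the documents.

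**Conclusion.** The gap is real and minor. The plan suggests cold to relieve the symptom that it is scoring and sets no order between the two. The exposure is mainly the 15–60 minute estimates. It is zero if no cold is used before the 60-minute score, and otherwise its size cannot be derived from the documents. Under the assumed one-sided inputs the 15-minute rate moves by 1.3 to 4.9 points; an equal 10–20% cut in all subjects lowers it by about 1.5 to 4.9 points.

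No secondary decision changes on the planning data. That rests on this product behaving like the comparator-filler study. A true 15-minute rate near the success line (50/80 = 62.5%) would make a few points matter, but the documents give no reason to expect one. The lower power figures for the primary should not be read as a finding that it is compromised, since they require cold before a score defined as immediate. The sample size stands.

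**What to change.** Add one sentence to Protocol 8.4.3:

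> On Day 1, no cold is applied after injection until the immediate VAS is recorded, and it is deferred until after the 60-minute VAS where possible; if used earlier it is applied identically to both folds, unless clinically needed on one fold, and its side and time are recorded.

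Deferral is better than a symmetry rule alone, because equal cold can still shrink the difference. No population needs changing: the mITT definition contains no ice exclusion. An analysis leaving out iced subjects is not advised, since icing can depend on the pain being scored.

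The cost is one sentence and a note of side and time when cold is used early. The downside is that early or one-sided comfort icing is restricted for up to 60 minutes. Sample size, endpoints and tests do not change.

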8.4.4 Blinding of Study Product

Injections of the study product prior to Week 24 are performed by the unblinded injecting investigator. The blinded evaluator is not allowed to retrieve study supplies or to be present during opening of the study supplies or during the injections. The injecting investigator is not to have any discussion with the blinded evaluator or subjects regarding the treatments.

Subjects are blinded to treatment assignment of each NLF. Subjects are physically masked (blindfolded) just prior to and during all injection procedures to prevent observation of the syringes containing study product.

Subjects, investigators, the sponsor’s staff conducting the study, and members of the administrative team will not have access to individual subjects’ treatment assignments. In the

event of an emergency that requires breaking of the study blind, randomization code envelopes will be maintained by each investigator that can be opened to reveal the study product.

See [Section 8.9.6.2](#) for a description of the method of unblinding a subject during the study if such action is warranted.

8.4.5 Method of Packaging, Labeling, Storage, and Dispensing

Study products will be supplied to the sites in their standard packaging. A label that includes the protocol number and Sponsor name will be attached to each pouch of the Revanesse Ultra + and Revanesse Ultra study products. Investigators will be instructed to follow instructions regarding storage in accordance with the products' [Instructions for Use](#).

All study products will be stored in a climate-controlled, limited access area.

The investigator agrees to store and administer the study products only at the site(s) listed on Form FDA 1572 (or investigator agreement/statement). The investigator, sub-investigator(s), or qualified designees also agree that the study products will be administered only to subjects who have provided written informed consent and have met all entry criteria. Study products may not be used for any purpose other than as stated in the protocol.

8.4.6 Study Product Accountability

Study products will be available on site for each subject. Receipt of study products will be documented and confirmed via the Investigational Product Receipt Form. All study products must be kept in a locked area with access restricted to designated study personnel in a climate-controlled, limited access area. The administration of study products will be recorded on the Study Product Dispensing Log. The site monitor will periodically check the supply of study products held by the investigator or pharmacist to ensure accountability. At study conclusion, all unused study products will be returned to the sponsor and documented using the Investigational Product Return Form.

Inventory records must be readily available for inspection by the study monitor and/or auditor, and open to inspection by regulatory authorities at any time.

8.4.7 Prior and Concomitant Medications/Treatments

All medications and other treatments taken by the subject within 6 months before Visit 1/Day 1 and during the study are to be recorded on the CRF using their generic name, if known, with the corresponding indication. The medications to be recorded include prescription and OTC medications and dietary supplements. All medications taken on a regular basis, including vitamins, aspirin, and acetaminophen, should be recorded prior to first use of the study medication.

The use of any concomitant medication must relate to the subject's documented medical history, prophylaxis, or an AE.

8.4.7.1 Medications, Supplements, and Other Substances Prohibited Before Study Entry and During the Study

The medications prohibited prior to Visit 1/Day 1 are listed in the exclusion criteria ([Section 8.3.2](#)).

Subjects will be advised to avoid the following for the duration of the study:

- Botox® in the study treatment areas
- Any chemical peel (light, medium or deep) in the study treatment areas
- Soft tissue augmentation anywhere on the face
- Dermabrasion or laser abrasion anywhere on the face
- Silicone injections or implants anywhere on the face
- Facial wrinkle therapies, including Accutane® and Renova®
- Aesthetic facial surgery (i.e., facelift)
- Oral corticosteroids or immunosuppressive medications
- Topical corticosteroids on the face
- Treatment with intense pulsed light

